## **3 DATA ANALYSIS CONSIDERATIONS**

### **3.1 General presentation of summaries and analyses**

Statistical analysis and generation of tables, figures, subject data listings, and statistical output will be performed using Statistical Analysis Software (SAS) Version 9.3 or higher. All tables and listings will use Courier New font size 9.

Descriptive statistics will be displayed to provide an overview of the study results. For continuous variables, descriptive statistics will include number of subjects with available measurements (n), mean, standard deviation (SD), median, minimum, and maximum.

For categorical variables, the number and percentage of subjects in each category will be presented. Unless otherwise noted, the denominator for percentages should be based on the number of subjects included in the respective analysis set. Subjects with missing data can generally be accounted for using either of the following approaches:

- For summaries of demographics and Baseline characteristics: summarize percentages based on all subjects in the analysis set and include a “Missing” category (corresponding to subjects

with missing data for the variable being summarized) as the last row in the list of categories being summarized.

- For summaries of efficacy and safety endpoints, unless otherwise specified: summarize percentages based only on those subjects with observed data for the variable being summarized. As the denominator may be different from the number of subjects in the analysis set being considered, the denominator should be displayed in the table. The general format for displaying this will be “n/Nsub (%)”.

Percentages will be presented to 1 decimal place. If the percentage is 100%, do not present a decimal. If the percentage is 0, do not present the percentage. Typically, the % sign should be presented in the column header, but not with each individual value.

For bimekizumab PK concentrations, summary statistics will include geometric mean, geometric coefficient of variation (CV), 95% confidence intervals for geometric mean, arithmetic mean, SD, median, minimum, and maximum. All summaries of PK variables will be based on the observed values. No imputation will be used.

Decimal places for descriptive statistics will always apply the following rules:

- “n” will be an integer
- Mean, SD, and median will use one additional decimal place compared to the original data
- CV [%] will be presented with one decimal place
- Minimum and maximum will have the same number of decimal places as the original value.

Derived variables in general will display the mean, SD and median to 1 more decimal place than the variables used in the derivation. If the number of decimal places reported in the raw data is varied then use either the maximum raw number of reported decimal places or 3, whichever is the lowest, as a guide for the descriptive statistics.

Statistical tests of efficacy variables will be presented as two-sided p-values rounded to three decimal places. P-values less than 0.001 will be presented as “<0.001” and p-values greater than 0.999 will be presented as “>0.999.” Statistical comparisons will be two-sided and will be performed at the 0.05 level of significance.

Per protocol, visit windows of  $\pm 3$  days from the first dose to Week 24,  $\pm 7$  days from Week 28 to Week 72 and  $\pm 14$  days from Week 76 to Week 144 are permissible. For the SFU Visit, visit window is 20 weeks  $\pm 7$  days from final dose.

Per protocol, visit windows of  $\pm 14$  days from the first OLE2 dose at all OLE2 visits except SFU2 are permissible, the SFU2 visit window is 20 weeks  $\pm 7$  days from final dose in OLE2.

All by-visit summaries will contain nominal (i.e. scheduled) visits only. Unscheduled visits will not be mapped to scheduled visits except for assessments that occur within a 3-day time window of a scheduled visit. In that case, the assessment will be mapped to the corresponding scheduled visit and will be used for the analysis. This will only occur for some vendor data.

A complete set of data listings containing all documented data as well as calculated data (e.g. change from Baseline) will be generated. Separate data listings will be generated for the OLE2 period.

## 3.2 Definition of Baseline values

A Baseline value for a subject is defined as the latest measurement for that subject up to and including the day of administration of first study medication, unless otherwise stated. If a Baseline assessment is taken on the same day as first administration of study medication, it is eligible to be used as the Baseline value, even in the case that the time of the assessment is recorded as taking place after the time of first study medication administration. This is considered acceptable as this measurement is still the best representation of the Baseline value of the given assessment since it is highly unlikely that the study medication could have an impact on any measurement in such a short period of time. However, such cases should be rare as study center personnel are instructed to do all assessments at the Baseline visit prior to administering study medication. One exception to this rule is plasma concentration. If Baseline plasma concentration is measured at a time after the first administration of study medication, then it should not be eligible to be considered as a Baseline plasma concentration. Such cases should be discussed with the quantitative clinical pharmacologist.

If a Baseline measurement is missing or not collected, and a Screening value is available, the Screening value will be utilized as Baseline instead.

Baseline values for component scores should be computed using components from the same visit where the relevant measurements were recorded prior to dosing. For example, if the Screening visit has all of the components, but the Baseline visit is missing one or more components, the Baseline value for the component score should be calculated using the Screening visit values.

When the time of first dose is derived, it should be based on the first injection of study treatment, regardless of whether or not it is an active treatment.

Unless specified otherwise, the process laid out above will always be followed to determine Baseline. An additional Baseline value for the OLE Period will be defined for anti-bimekizumab antibodies for subjects initially randomized to secukinumab and for selected summaries of laboratory evaluations. This baseline for the OLE Period is the latest measurement on/prior to the day of first dose in the OLE Period for subjects switching from secukinumab to bimekizumab.

Note that for any laboratory value that occurs on the day of treatment switch, that lab value will be attributed and summarized for the treatment the subjects were on previously.

For subjects enrolled in OLE2, the OLE2 first dose will be administered at the Week 144/OLE2 Baseline Visit and data collected at this visit will be used as baseline data for safety data in the OLE2 Period. Efficacy data will continue to use the Week 0 Visit as Baseline.

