- A shift table of the number and percentage of subjects experiencing CTCAE grade 0, 1, 2, 3, or 4 values (as applicable) at Baseline to minimum/maximum post-Baseline CTCAE grade, by laboratory variable and treatment group. Two separate tables will show results for the initial treatment period (for the SS) and the Initial and Maintenance Treatment Period (for the MS). An additional table for the OLE period will be provided for the OLS by treatment the subjects were receiving at the time of the assessment of the value with the given CTCAE grade. A lipid profile table of treatment emergent markedly abnormal laboratory data will be provided for the Initial and Maintenance Treatment Period (SS) and the Open-label Extension treatment period (OLS) separately.

In addition, a shift table of number and percentage of subjects experiencing post-Baseline HDL Low risk ( $\geq 1.55$  mmol/L), Intermediate risk ( $\geq 1.04 - < 1.55$  mmol/L) and High risk ( $< 1.04$  mmol/L) compared to baseline will be provided for the Initial and Maintenance Treatment Period (SS) and the Open-Label Extension Treatment Period (OLS).

Shift laboratory summaries will use the Baseline for Open-Label Extension Period for subjects switching from secukinumab to Bimekizumab as described in Section 3.2.

A figure of neutrophil values over time for subjects with at least one markedly abnormal neutrophil value (CTCAE Grade 3 or 4) will also be presented.

A by-subject listing of all laboratory data (including urinalysis) will be provided. Separate by-subject listings for the OLE and the OLE2 treatment periods will be provided. These listings will be presented by treatment group and will include: center, subject identifier, age, sex, race, weight, visit, laboratory variable, result (with abnormal values flagged as “L” or “H” accordingly) and unit.

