## **10.4 Vital signs, physical findings, and other observations related to safety**

### **10.4.1 Vital signs**

The following vital signs variables should be summarized: systolic blood pressure (mmHg), diastolic blood pressure (mmHg), body temperature (°C) and heart rate (beats/min). The following summary will be provided for the Initial Treatment Period (SS) for Initial and Maintenance Treatment Period, and for the Open-Label Extension Period (OLS). Vital signs will not be summarized for the OLE2.

- A summary of the absolute and change from Baseline value for each vital sign variable by treatment group and visit.

- A shift from Baseline to Post-Baseline systolic and diastolic blood pressure values based on the following categorization will be provided for the Initial and Maintenance Treatment Period (SS), and the Open-label Extension Period (OLS):
  - Hypotension: systolic blood pressure <90 mmHg *or* diastolic blood pressure <60
  - Normal: systolic blood pressure  $\geq 90$  and <120 mmHg *and* diastolic blood pressure  $\geq 60$  and <80 mmHg
  - Elevated: systolic blood pressure between 120-129 mmHg *and* diastolic blood pressure <80
  - Stage 1: systolic blood pressure between 130-139 mmHg *or* diastolic blood pressure between 80-89
  - Stage 2: systolic blood pressure  $\geq 140$  and  $\leq 180$  mmHg *or* diastolic blood pressure  $\geq 90$  and  $\leq 120$  mmHg
  - Hypertensive crisis: systolic blood pressure >180 mmHg *and/or* diastolic blood pressure >120 mmHg.

The following summary will be provided for the Initial Treatment Period (SS), the Initial and Maintenance Treatment Period (SS), and the open-Label Extension Period (OLS):

- A summary of the number and percentage of subjects experiencing at least one markedly abnormal value for a vital sign variable as defined in [Table 10–4](#), by treatment group.

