#### 10.4.3 Electrocardiograms

ECG data will be analyzed by treatment group and visit for the Initial Treatment Period (SS), the Initial and Maintenance Treatment Period (SS), and by treatment sequence for the Open-Label Extension Period (OLS).

A summary of the number and percentage of subjects with normal and abnormal ECG results, as determined by the central reader, will be presented for all applicable visits.

The following ECG variables will be summarized (absolute values and change from Baseline) by visit: QTcF, RR, PR, QRS and QT.

QTc outliers are defined as QTcF values following dosing that are greater than 450 ms or are increases from Baseline greater than 30 ms. QTcF outliers will be highlighted in the data listings and summarized using the following categories:

- Values >450 ms, >480 ms, >500 ms
- Increase from Baseline of >30 ms, increase from Baseline of >60 ms, increase from Baseline of >90 ms
- Values >450 ms and increases of >30 ms. Values >500 ms and increases of >60 ms

The number and percentage of subjects who meet the ECG outlier criteria at any assessment post first dose will be summarized.

Two separate by-subject listing of all 12-lead ECG data will be provided based on interpretation from central reader and from site.

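### For subjects who switch from secukinumab, open-label vital-sign, ECG and PHQ-9 changes are measured from Week 0, so change since starting bimekizumab is not separated from change on secukinumab

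*SAP*

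**What the plan says.** The default in SAP Section 3.2 reads: "A Baseline value for a subject is defined as the latest measurement for that subject up to and including the day of administration of first" (the first dose of IMP is meant). For a subject randomized to secukinumab, that is the value before the first secukinumab dose. The default binds: "Unless specified otherwise, the process laid out above will always be followed to determine Baseline".

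The same section adds one exception for the OLE: "An additional Baseline value for the OLE Period will be defined for anti-bimekizumab antibodies for subjects initially randomized to secukinumab and for selected summaries" (laboratory ones). This OLE Baseline is the latest value on or before the first OLE dose, for subjects moving from secukinumab to bimekizumab. Section 10.3 puts it to use: "Shift laboratory summaries will use the Baseline for Open-Label Extension Period for subjects switching from secukinumab to Bimekizumab as described in Section 3.2".

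Section 3.2 also resets the reference at entry to the second extension (OLE2), where "data collected at this visit will be used as baseline data for safety data in the OLE2 Period".

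Three other safety sections plan OLE summaries on the Open-Label Set that use Baseline, and none names the OLE Baseline:

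- Section 10.4.1 asks for "A summary of the absolute and change from Baseline value for each vital sign variable by treatment group and visit", a blood-pressure category shift, and the markedly abnormal criteria of Table 10–4, which pair an absolute limit with a change from Baseline.
- Section 10.4.3 summarizes ECG change from Baseline and states: "QTc outliers are defined as QTcF values following dosing that are greater than 450 ms or are increases from Baseline greater than 30 ms".
- Section 10.4.4.5 tabulates PHQ-9 change from Baseline for the Open-Label Set.

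Section 3.6 presents ECG, PHQ-9 and vital signs in the OLE by treatment sequence. Prior-secukinumab subjects have separate columns, and there is also an All Subjects column.

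**The concern.** One of the objectives in Section 2.1.3 is the safety of starting bimekizumab in subjects who had secukinumab in the double-blind period. The natural reference for that question is the last value before the first bimekizumab dose. The SAP uses that reference for laboratory shifts in these subjects, but not for blood pressure, QTcF or PHQ-9.

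With Week 0 as reference, each OLE change in a switcher is the sum of two parts: what happened on secukinumab and what happened afterwards. A criterion that requires an increase or decrease can then be met by the first part alone. It can also fail because the first part went the other way and cancelled the second. A missed rise is the more serious case, since the table meant to show it would not.

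**Working it through.** The SAP states no figure on this point, so there is none to reproduce. The check traces the baseline rule and then applies the SAP's criteria to example values.

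**Step 1. Which OLE outputs depend on Baseline?**

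| OLE output | SAP section | Uses Baseline? | Reference for switchers |
|---|---|---|---|
| Laboratory shift | 10.3 | yes | OLE Baseline |
| Vital-sign change, blood-pressure shift | 10.4.1 | yes | Week 0 |
| Markedly abnormal blood pressure | Table 10–4 | yes, with an absolute limit | Week 0 |
| ECG change, QTcF increase >30, >60, >90 ms | 10.4.3 | yes | Week 0 |
| PHQ-9 change | 10.4.4.5 | yes | Week 0 |
| QTcF >450, >480, >500 ms | 10.4.3 | no | not applicable |
| PHQ-9 ≥15, ≥20 | 10.4.4.5 | no | not applicable |
| Laboratory markedly abnormal values | 10.3 | no | not applicable |
| eC-SSRS incidence, adverse events | 10.4.4.2, 10.2 | no | not applicable |

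**Step 2. The identity.** Write W0 for the Week 0 value, S for the last value on or before the first OLE dose, and X for an OLE value.

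X − W0 = (S − W0) + (X − S)

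The question about starting bimekizumab concerns X − S. The SAP's tables use X − W0.

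**Step 3. The SAP's criteria on example values.** The thresholds come from Table 10–4 (systolic >180 with an increase ≥20; diastolic >105 with an increase ≥15) and Section 10.4.3 (QTcF increase >30 ms). The subject values are invented, because the SAP gives no data.

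| Variable | W0 | S | X | X − W0 | Flagged from Week 0 | X − S | Flagged from switch |
|---|---|---|---|---|---|---|---|
| Systolic | 160 | 182 | 183 | +23 | yes | +1 | no |
| Systolic | 165 | 150 | 182 | +17 | no | +32 | yes |
| Diastolic | 100 | 80 | 106 | +6 | no | +26 | yes |
| QTcF (ms) | 400 | 432 | 433 | +33 | yes | +1 | no |
| QTcF (ms) | 420 | 400 | 435 | +15 | no | +35 | yes |

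The classification changes in both directions. Means behave the same way: a mean PHQ-9 change of −2 on secukinumab and +1.5 on bimekizumab would appear in the OLE column as −2 + 1.5 = −0.5.

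**Step 4. Direction of the effect for QTcF, under assumptions.** Assume that bimekizumab has no effect. Let the drift on secukinumab have mean d and between-subject SD 8 ms and persist into the OLE, and let visit-to-visit noise have SD σ. Then:

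- P(increase >30 ms from Week 0) = 1 − Φ[(30 − d)/√(2σ² + 8²)]
- P(increase >30 ms from switch) = 1 − Φ[30/√(2σ²)]

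A simulation of 400,000 subjects per setting gave the following and agrees with these formulas to within 0.1 percentage point.

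| d (ms) | σ (ms) | From Week 0 | From switch |
|---|---|---|---|
| 0 | 8 | 1.5% | 0.4% |
| 0 | 12 | 5.5% | 3.9% |
| 5 | 8 | 3.6% | 0.4% |
| 5 | 12 | 9.1% | 3.9% |
| 10 | 8 | 7.5% | 0.4% |
| 10 | 12 | 14.3% | 3.8% |

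Even with zero mean drift, individual drift adds flags from Week 0. The switch baseline is not free of noise either. d, the drift SD and σ are all assumed, so the table shows direction only.

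**Step 5. How many subjects does the rule cover?** Section 2.4 plans 350 subjects on secukinumab. That is the ceiling on switchers whose OLE changes are referred to Week 0. It does not count those whose classification would differ.

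**The case against.** The strongest defence is that the choice is stated rather than overlooked. Section 3.2 names its exceptions and says the default otherwise holds. A common Week 0 reference keeps all sequences and the All Subjects column on one scale, and change from Week 0 truly describes the sequence secukinumab then bimekizumab. The tables are descriptive. Group-level drift on secukinumab can be read from the vital-sign, ECG and PHQ-9 tables through Week 48, although in the Safety Set rather than the Open-Label Set. All of this stands. It does not supply the subject-level change since the switch, which the shift and increase criteria are meant to classify.

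A reader might infer more than the SAP supports, in four ways:

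- *That secukinumab-period changes will be presented simply as bimekizumab findings.* Section 3.6 puts switchers in their own sequence columns. The mixing lies within those columns and in All Subjects. Section 10.4.1 says treatment group rather than sequence, a small mismatch with Section 3.6.
- *That OLE safety reporting as a whole rests on Week 0.* Step 1 shows it does not. For adverse events, Section 10.2 attributes post-switch events to the new treatment, apart from its rules for events on the switch date. Section 10.2.2 splits switchers' events at 140 days after the last secukinumab dose. Those analyses serve the Section 2.1.3 objective directly.
- *That the OLE2 rule shows the same three variables handled in the opposite way.* The OLE2 reset yields no summary tables for them. Section 10.4.1 excludes OLE2 vital-sign summaries, Section 10.4.3 plans ECG tables only as far as the OLE, and PHQ-9 in OLE2 is a listing. The useful precedent is the laboratory shift rule.
- *That a known number of subjects will be misclassified.* The SAP gives no drift or variance from which to compute one.

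**Conclusion.** The point holds in limited form. For subjects switching from secukinumab, the OLE summaries of vital-sign change, blood-pressure shift, markedly abnormal blood pressure, ECG change, QTcF increase and PHQ-9 change use Week 0. They combine change on secukinumab with change on bimekizumab in the switcher columns and in All Subjects. Individual changes since the switch can be falsely flagged or missed.

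That Week 0 is the reference follows from the text of Section 3.2 without further assumption. The size of the effect is unknown: at most the planned 350 secukinumab subjects fall under the rule, and the fraction reclassified depends on drift and noise that the SAP does not give. Efficacy, absolute-value criteria, laboratory markedly abnormal values, eC-SSRS and adverse-event tables are untouched. This is a cheap improvement to descriptive safety tables that would make them answer a stated objective.

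**What to change.** In Section 3.2, extend the existing OLE Baseline (latest value on or before the first OLE dose) to the vital-sign, ECG and PHQ-9 change, shift and increase/decrease summaries in the secukinumab-to-bimekizumab columns. Cross-reference it in Sections 10.4.1, 10.4.3 and 10.4.4.5.

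Keep Week 0 for subjects on bimekizumab throughout, for efficacy, and for the All Subjects column or as a supportive version. Footnote each table with the baseline used.

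The cost is SAP wording, a derivation whose rule is already defined for laboratory data, and one more set of descriptive summaries. Baseline visits will differ between columns, which the footnote must make plain. One point needs checking against the protocol's assessment schedule: whether each of these measures has a value close to the first OLE dose. If not, the latest earlier value may fall well before Week 48.

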## 3.3 Mapping of data from early withdrawal visits

If the early withdrawal visit (PEOT visit) occurs at a scheduled visit as outlined in the schedule of assessments, then no mapping is necessary and any early withdrawal assessments should correspond to that scheduled visit. Premature visits that occur between scheduled visits will be assigned to the next scheduled visit. This approach means that there is a chance that data collected will be mapped to a visit where the given assessment would not have been collected as per the protocol schedule of assessments. Such data would not be summarized in by-visit tables (though it would be available in the listings).

The only exception to the above rule is for anti-bimekizumab antibody assessments, in which all early withdrawal visit assessments will be assigned to the next scheduled visit at which anti-bimekizumab antibody are assessed.

All by-visit summaries will contain scheduled visits only. Unscheduled visits will not be mapped to scheduled visits. Note that based on the early withdrawal mapping conventions described above, a mapped early withdrawal visit is considered as observed at that visit and should be summarized as such in the tables.

### **3.4 Protocol deviations**

Important protocol deviations are deviations from the protocol which potentially could have a meaningful impact on study conduct, or on the primary efficacy, key safety, or PK outcomes for an individual subject. The criteria for identifying important protocol deviations will be defined within the appropriate protocol-specific document at study start. Important protocol deviations will be reviewed as part of the ongoing data cleaning process. Important protocol deviations including those that lead to exclusion from the analysis sets will be identified and documented prior to unblinding.

Deviations related to the Coronavirus Disease 2019 (COVID-19) global pandemic are unavoidable deviations from the protocol due to confirmed COVID-19 infection, suspected COVID-19 infection, general circumstances around COVID-19 without infection or any other deviation from the protocol due to COVID-19. COVID-19 protocol deviations will also be reviewed separately as part of the ongoing data cleaning process.

